Group Procedures. Group is organized for families to receive information about social communication, emotional regulation, play development, and behavioral challenges in toddler playgroups in a relaxed, supportive, child-friendly setting that provides the opportunity to talk with a professional and meet other parents. Group is designed to provide parents with resources and supports for their child through weekly small parent group meetings using a curriculum to help parents focus their attention on their child's developmental needs. Handouts with activities for the parents and children to participate in during the month will be provided and samples are included in the Appendix. Group is different than Individual because it does not provide individualized intervention, does not provide direct instruction to the parent in the home on how to implement strategies and supports, and does not ensure treatment fidelity or the level of intensity. Up to 12 families will attend each group, with a blend of children with early risk for ASD ranging in age from 12 to 24 months. The groups are guided by an interventionist from psychology or a related discipline and meet for 9 months during the intervention period and monthly follow-up sessions with parents through the child's 36 month birthday. Information is provided to families through discussion and handouts, answering questions, describing scenarios, and making suggestions. Little documentation on generalization of group education training for parents is available. Kaiser and colleagues concluded that while there was variability in the speed and consistency of learning that occurred by parents, it took an average of 20 individualized clinical sessions prior to generalized use of the procedures in the home setting. In a large-scale review of empirical studies of parent implemented interventions for young children with communication disorders, including ASD, Hancock and Kaiser identify generalization of the intervention strategies by parents into the home environment as key. Thus, we have designed Group to provide helpful information and support to families; however, we do not anticipate that families will generalize the use of intervention strategies to activities at home from the education meeting.

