Individual Procedures. Individual teaches parents how to support their child's communication, social, and play skills in everyday routines, activities, and places. The clinician meets with parents for 2 home visits per week for 9 months. Individual is organized by phases, beginning with the initial home visit, a month of program planning, 6 months of intervention implementation, and 2 months of generalization. The initial home visit is designed to provide an overview of Individual to the family and to discuss the importance of intensive intervention, defined as active and productive engagement for 20-25 hours per week for children with ASD. The program planning phase entails completing the SCERTS Assessment Process (SAP), which is a curricular-based assessment using parent report and observation for children with ASD 60 to identify goals and objectives for the child and teaching strategies and supports for the parents. The program planning phase is completed by mapping out which objectives will be targeted in which routines and activities to total 5 hours a day, 5 days a week. Some assessment forms are included in the Appendix, others have been added to the IRB Smartform. The parent who is the primary caregiver will be the focus of Individual training. If both the mother and father or an extended family member share caregiving, then they can participate as long as they can attend Individual sessions regularly and are available for the home observation. In the implementation phase, the 2 weekly sessions will include the following three components: 1) setting the stage to briefly review and revise the agenda for that visit and gather updates; 2) intervention implementation with the following steps: a) review the objective, b) use modeling, guided practice, or video review to teach the strategy, c) provide feedback to the parent, and d) problem solving and plan for next time; steps a-d are repeated for 3 to 5 activities per session; and 3) summarize plans for parent implementation between sessions and data collection using ESI Daily Intervention Log. During generalization, the clinician meets with the family in a variety of community settings to teach the parent how to implement strategies in new settings.

Measures/Handouts/Guides

Parent Questionnaires Completed Monthly from 12-36 Months
Baby Siblings Research Consortium Inventory History Form
Parent Questionnaires Completed Monthly every 6 Months from
12-36 Months

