Data Analytic Strategy. The main research aims and hypotheses will be analyzed using a series of mixed models, focusing on Growth Curve Modeling (GCM) and Random-Effects Regression (RER) as more powerful alternatives to repeated measures ANOVA, and estimates of effect sizes will be obtained. We anticipate that effect size estimates will be conservatively derived from simple inspection of observed differences in treatment versus control means divided by the appropriate standardizer (either the control standard deviation or the pooled standard deviation, depending upon whether the treatment is inducing group differences in variances or not). The research aims compare growth trajectories (or residualized change, or outcome only, depending on the dependent variable of interest) for children in the treatment and control groups. It is hypothesized that children receiving the Group plus Individual condition will show significantly faster growth trajectories or change on the MAETS, which will mediate social communication, autism symptoms, developmental level, and adaptive behavior outcomes. Unconditional models that vary in complexity will be used to determine the most parsimonious models for estimating growth in this sample. After fitting the overall model, we will perform fixed-effects contrasts to test for cross-sectional differences between the two groups at points along the curve. Aims 2 and 3 build upon these models to investigate potential mediator and moderator variables that may predict response to treatment. Moderator variables such as initial level of child or parent performance and measures of family functioning will be interacted with treatment group to investigate potential moderating relationships. To investigate potential mediators of treatment effectiveness such as MAETS, we will follow standard strategy for testing mediational effects in a multilevel design where fidelity is conceptualized as a level 1 mediator that can vary by time. Finally, we will consider the possibility that the mediated relation may be stronger in one subgroup than the other (moderated mediation), either because treatment fidelity is accomplished to a greater extent in one subgroup than another or because the link between treatment fidelity and outcome is stronger in one subgroup than another (e.g., treatment fidelity predicts outcome only in individuals with sufficient cognitive abilities). In addition to existing GCM/RER analyses, in synergy with Projects I & II we will repeat our analyses using Functional Data Analysis, a new approach that significantly improves both the detection of common features in trajectory shape as well as the identification of individual spurts or delays relative to the group. Project III will rely on the Data Management and Analysis Core for data storage, management, and transmission to NDAR.

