
Attrition Analyses. All analysis will be done using an intention to treat approach. That is, every subject in the study will be considered in the analysis as a member of the treatment group to which s/he was assigned. We will conduct a series of analyses to examine attrition and its potential effect on the results ⁶⁹, including examining the differential attrition rates for the two treatments and for child and parent characteristics of those completing and those who did not complete one or both treatment conditions, different definitions of dropout, different outcome measures, and treatment-correlated attrition. For the HLM analyses with multiple time points, missing data are not a concern, but differential attrition by treatment group would be. If differential attrition appeared to be a problem, then we would conduct multiple imputation of missing data ⁹⁵ to attempt to estimate the appropriate effect sizes and confidence intervals.

Power Analyses. Power for growth curve modeling was estimated using a power estimation program developed for HLM models 61. When estimating power in growth curve models, there are a number of factors that need to be considered. In addition to alpha level, number of subjects, and anticipated effect size, power can also vary as a function of the number of observations employed and the duration of the study. For these power analyses, we set alpha at .05 and we anticipated as few as 5 and as many as 25 observations per child (per measure). Additionally, we estimated that there would be approximately 10 times as much within person variability than between person variability (the ICC for the person level effect would be .10). Using these estimates, we anticipate that 92 subjects would give us a power=.90 to detect an effect of d=.50 (which corresponds to a medium effect) with five time points estimating linear change. For models testing treatment differences in the presence of quadratic change (with 15 or more assessments per child), power is .95. If attrition drops the sample size to 80 subjects, we will still have power equal to .86 to detect a medium-sized effect (with five assessments estimating linear change) and power=. 91 for those treatment differences tested in the presence of quadratic change. Thus, the minimum power to detect medium effects with 80 subjects is .86. We anticipate that the use of FDA and PACE will increase power.

7. Risks

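### The Aim 1 models and the power calculation have no term for home-visit clinician or playgroup, so if outcomes cluster by clinician the standard errors are too small and the .90/.86 power is optimistic

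*Combined protocol and SAP*

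**What the plan says.** Section 5, Group Procedures, describes a weekly parent group led by an interventionist over the 9-month intervention period: "Up to 12 families will attend each group". The text that follows adds that typically developing community volunteers also attend. Both arms receive Group. Individual Procedures applies to the experimental arm only: "The clinician meets with parents for 2 home visits per week for 9 months".

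Section 6, Data Analytic Strategy, says the main aims and hypotheses "will be analyzed using a series of mixed models, focusing on Growth Curve Modeling (GCM) and Random-Effects Regression (RER"). It names no effect for playgroup, interventionist or clinician. Under Power Analyses, "For these power analyses, we set alpha at .05", and the result is that "92 subjects would give us a power=.90 to detect an effect of d=.50". With 80 children, "we will still have power equal to .86 to detect a medium-sized effect". The only ICC given is .10 at the person level. It describes repeated measures within a child, not similarity between children.

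The protocol does not state whether playgroups are separate by arm, how many study children each holds, how many home-visit clinicians there are, or how many families each clinician serves.

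**The concern.** Children treated by the same clinician may do better or worse together, because clinicians differ in skill. If the model ignores this, it treats the experimental-arm children as more independent than they are. The standard error of the treatment effect is then too small, the test rejects too often under the null, and the stated power is not delivered. The results of a few strong clinicians could also be credited to the programme.

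The plan itself expects delivery to vary by provider: Fidelity and Program Evaluation Procedures has clinicians rated regularly and given feedback on deviations. That variation is monitored but does not enter the analysis.

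**Working it through.** **Inputs from the protocol.** Alpha .05 (sidedness not stated; two-sided assumed). Power .90 at N = 92 and .86 at N = 80 for d = .50. Two arms (ratio not stated; 1:1 assumed, so 46 per arm).

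**Assumed, because not given.** Families per clinician m = 12 or 6. Cluster ICC .01 to .10, defined on the variance of the child-level estimate (for example, a child's slope).

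**The plan's own figures.** The absolute values could not be reproduced by standard readings. For example, a simple comparison of two means with d = .50 gives .67 and .61. The scale of d and the slope variance are not given, so this does not show that the figures are wrong. They do agree with each other: (1.96 + 1.28) × √(80/92) − 1.96 = 1.06, giving power .856 against the stated .86. Sample size alone explains the change, and no separate cluster term is visible. The calculation below takes .90 and .86 as correct and scales them.

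**Are clinicians shared?** This is not stated, but recruitment is 46 children a year for two years, so about 23 a year in the experimental arm. With 9 months of treatment and even recruitment, about 23 × 9/12 ≈ 17 families are in treatment at once, needing about 34 home visits a week. A different clinician for each of 46 families is not plausible.

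**Clinician clustering, experimental arm only.** The design effect averages a clustered and an unclustered arm: DE = 1 + (m − 1) × ICC / 2.

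- True type I error of the unadjusted test = 2 × [1 − Φ(1.96/√DE)].
- Power = Φ[(1.96 + z_power)/√DE − 1.96], with z_power = 1.28 for .90 and 1.08 for .86.

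For m = 12 and ICC .05: DE = 1 + 11 × .05/2 = 1.275 and √DE = 1.129. Type I error uses 1.96/1.129 = 1.736, giving .083. Power uses 3.24/1.129 − 1.96 = .91, giving .82.

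| Families per clinician | ICC | DE | Type I error | .90 (N = 92) becomes | .86 (N = 80) becomes |
|---|---|---|---|---|---|
| 12 | .01 | 1.055 | .056 | .88 | .84 |
| 12 | .05 | 1.275 | .083 | .82 | .77 |
| 12 | .10 | 1.550 | .115 | .74 | .69 |
| 6 | .05 | 1.125 | .065 | .86 | .82 |

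**Playgroup clustering depends on a fact the protocol omits.**

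- If playgroups are arm-specific, with 12 study children each and ICC .05, DE = 1 + 11 × .05 = 1.55. Type I error is .115, and power falls from .90 to .74 and from .86 to .69.
- If playgroups mix arms, the playgroup effect largely cancels from the treatment contrast, and the variance factor is 1 − ICC = .95. There is no power loss (about .91 if the playgroup effect is fitted), and an unadjusted test is slightly conservative (type I error about .044).

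**Few clusters.** These figures use a normal approximation. At 12 families each, 46/12 is about four clinicians, so a test with suitable degrees of freedom would lose more. For scale, arm-specific playgroups of 12 at ICC .05, tested on 6 degrees of freedom, give power of about .59 rather than .74. Much of that drop comes from the degrees of freedom: the same test at ICC zero gives .77.

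**The case against.** Several objections have force.

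- A reader might infer that the standard errors are certainly too small and the power certainly overstated. The documents do not support this. It needs a positive ICC and clusters that lie within one arm, and neither is stated.
- A reader might also take the both-arm figures (.74, or .61 at ICC .10) as the expected loss. They rest on arm-specific playgroups, which appear nowhere in the text.
- Twelve is a ceiling on playgroup size that may include volunteers. It is not a clinician caseload; its use as one above is an assumption, which is why 6 is shown too.
- The Aim 1 random-effects structure is left open rather than specified as visits within child and nothing else. The point is that no cluster term is named, not that one is ruled out. Delivery details may also lie in the treatment manual, which was not available here.
- The ICC scale matters. Under the plan's split (person .10, within-person .90), a mean of five visits has variance .10 + .90/5 = .28. If .05 means a share of between-child variance only, the effective ICC is .05 × .10/.28 = .018. With m = 12 in one arm, DE is about 1.10, power about .87 and type I error about .06.
- A manual and regular fidelity feedback make a low ICC plausible. At .01 the loss is only .90 to .88.

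These objections limit the certainty and the size. They do not remove the core point: mixing arms in the playgroups cannot cancel a clinician effect that exists in one arm only.

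**Conclusion.** The point holds in conditional form. The plan names no clinician or playgroup term in either the Aim 1 models or the power calculation, while experimental-arm families very probably share clinicians. With a positive clinician ICC, the treatment test is too liberal and the stated power is optimistic. Over the assumed ICC range of .01 to .10 with 12 families per clinician, the effect runs from minor (.90 to .88, type I error .056) to material (.90 to .74, type I error .115). Smaller caseloads reduce it and few clinicians increase it. Whether playgroups add anything cannot be settled from the documents. The adjusted powers are scaled from .90 and .86 as stated, so they show the likely size of the problem and should not be read to the second decimal.

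**What to change.** Record the home-visit clinician and the playgroup for every family, and state whether playgroups mix arms.

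Fit the Aim 1 models with a clinician random effect in the experimental arm only (a partially nested model) and a playgroup effect, using small-sample degrees of freedom such as Kenward-Roger. Because Aim 1 compares trajectories, allow the clinician effect on the slope as well as the intercept where it can be estimated. If there are too few clinicians to estimate the variance, prespecify the partially nested model as a sensitivity analysis. If playgroup membership changes as families join and leave, say how it will be coded.

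Restate the .90 and .86 power as a range over stated caseloads and cluster ICCs, and define the scale of the ICC.

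The cost is two recorded identifiers and changes to the SAP wording. Intervals will be wider (by a factor of about √1.55 = 1.25 if playgroups of 12 are arm-specific and the ICC is .05), and the stated power will look less favourable. No extra families are needed. The identifiers should be captured during delivery, because they may be hard to reconstruct afterwards.

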In response to RFA-HD-12-195, this treatment project is designed to address two significant public health challenges- the need for validated, manualized treatments for young children with ASD that are cost-efficient and feasible for community-based implementation, and the need to reduce the age of entry into early intervention. The major objective is to directly compare two parent intervention conditions for 9 months: 1) an information, education and support group (Group) offered weekly, and 2) an individualized parent-implemented intervention (Individual) offered in 2 weekly sessions to teach parents how to embed strategies to support social communication skills within everyday routines, activities, and places. The Emory ACE Center will recruit 92 parent-infant dyads at 12 months of age from theboth high and low risk siblings being studied. Inclusion criteria for high risk infants will be a positive screen on 2 of 4screening measures indicating the presence of diagnostic features of ASD by 12 months of age. Inclusion criteria for low risk infants will be a positive screen on 2 of 4 screening measures indicating the presence of diagnostic features of ASD by 12 months of age. Families will be randomly assigned to either Group or Group +Individual for 9 months. Outcome measures of social communication, autism symptoms, developmental level, and adaptive behavior will be gathered every 6 months from 12 to 36 months of age to measure treatment and follow-up effects. Measures of parent transactional support and child active engagement will be collected monthly beginning at 12 months until 36 months of age to examine change in developmental trajectories.

This project is conceptualized as a series of research questions (RQ) for each specific aim to examine the effects of intervention on outcomes of toddlers with ASD. The specific aims and research questions are:

Aim 1. Effectiveness of Treatment: To compare the effects of Group alone to Group plus Individual implemented from 12 to 21 months of age on outcome measures of social communication skills, autism symptoms, developmental levels, and adaptive behavior from 12 to 36 months. Research will address specific questions with regard to whether there are: RQ1a) differences in growth trajectories from 12 to 36 months on social communication skills and autism symptoms, and RQ1b) differences in trajectories of developmental level and adaptive behavior from 12 to 36 months for children receiving

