Group alone versus Group plus Individual for 9 months from 12 to 21 months of age. Although the treatment group may qualify at 12 months of age, treatment bay begin up to age 15 months.

- Aim 2. Mediators of Treatment: To determine whether parent transactional support and child active engagement are mediators of response to intervention. Specific research questions will address whether: RQ2a) there are differences in trajectories of parent's use of transactional supports and child's level of active engagement during everyday activities with their child during intervention and follow-up booster sessions until 36 months of age for parents participating in Group alone and Group +Individual, and RQ2b) the degree of parent transactional support and child active engagement predict change in children's social communication skills and severity of autism symptoms between at 18, 24 and 36 months of age.
- Aim 3. Moderators of Treatment: To identify individual child and family characteristics which predict response to intervention. Specific research questions will address: RQ3a) what moderator variables predict response Group, and RQ3b) what moderator variables predict response to Group +Individual?

The expected outcomes of this study will have the following important implications: 1) documentation of improved outcomes for very young toddlers with ASD receiving a manualized, community-based, cost efficient, appropriate, and effective intervention; 2) evidence that parent individualized intervention beginning by 12 months of age leads to better outcomes than group education and support; and 3) substantiation of the critical need for screening and identification of ASD in the 2nd year of life, rather than waiting until the 3rd year or later, because this may be a crucial developmental period for effective early intervention.

5. Study Design, Methods and Participant Selection

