The following dependent variables will be collected by the CAC and coded by raters blind to treatment condition before treatment at 12 months and again at 24 months and 36 months of age. Additionally, the Social Communication Measures will be completed at 15 months and 21 months of age for all children enrolled into the Early Social Interaction project.

Social Communication Measures. The Communication and Symbolic Behavior Scales (CSBS) Behavior Sample will be video recorded to measure social communication. Reliability and validity of the CSBS has been reported (see CAC). The raw scores will be summed to form a social, speech, and symbolic composite.

Autism Symptoms. The Autism Diagnostic Observation Schedule (ADOS) (see CAC) is the gold standard diagnostic measure of ASD. The revised algorithms forming Social-Affect and Restricted Repetitive Behavior ratings of autism symptoms will be used.

Developmental Levels. The Mullen Scales of Early Learning MSEL (see CAC) measures developmental level with separate scores for four cognitive scales that form an early learning composite. A nonverbal DQ based on age equivalent divided by chronological age multiplied by 100 will be calculated from the average of the Fine Motor and Visual Reception scales and a verbal DQ will be calculated from the Receptive and Expressive Language scales.

Adaptive Behavior. The Vineland Adaptive Behavior Scales *VABS-II* (Survey Interview Form; see CAC) yields a standard score in four domains— Communication, Daily Living, Social, and Motor, and an Adaptive Behavior Composite.

Expressive Language Phase. The child's expressive language phase will be determined at each assessment based on the benchmarks delineated by Tager-Flusberg and colleagues and recommended for evaluating the efficacy and comparing outcomes across NIH-funded intervention studies. Based on multiple sources of information about language benchmarks, the language will be categorized as: *Preverbal Communication, First Words, Word Combinations, or Sentences, to* provide a clinically meaningful measure of language outcome.

Mediator Variables

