With the infrastructure available for the Emory ACE Center, in collaboration with the FSU Autism Institute, this new collaborative team will be able to implement a large-scale treatment study of one of the youngest samples of children with diagnostic features of ASD. The expected impact of this study will: 1) document improved outcomes for the youngest sample of children with ASD receiving a manualized, cost efficient, appropriate, and effective intervention that is implemented in community-based settings; and 2) substantiate that individualized intervention beginning by 12 months of age leads to better outcomes, providing evidence that early detection of autism is crucial to enable access to early intervention.

6. Statistical Analysis

Data Analyses and Power

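### Aim 1 has no primary outcome or multiplicity rule, and the stated minimum power assumes five assessments where the Dependent Variables section schedules three for three of the four domains.

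*Combined protocol and SAP*

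**What the plan says.** Objectives (section 4) sets two Aim 1 questions side by side, with no ranking: "differences in growth trajectories from 12 to 36 months on social communication skills and autism symptoms" (RQ1a) and "differences in trajectories of developmental level and adaptive behavior from 12 to 36 months" (RQ1b). That makes four domains. The opening summary adds a fifth, social visual engagement.

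The Dependent Variables part of section 5 lists several scores per domain and does not say which will be tested. For the CSBS, "The raw scores will be summed to form a social, speech, and symbolic composite". The ADOS gives two ratings. The Mullen gives "separate scores for four cognitive scales that form an early learning composite" plus verbal and nonverbal DQs. The Vineland gives four domain scores and a composite. A categorical expressive language phase is listed as well.

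Data Analytic Strategy (section 6) says: "The main research aims and hypotheses will be analyzed using a series of mixed models". It then adds contrasts between the arms at unnamed points on the curve, and a repeat by Functional Data Analysis. On the form of comparison it says: "The research aims compare growth trajectories (or residualized change, or outcome only, depending on the dependent variable of interest". No text calls any outcome primary or describes a multiplicity adjustment. Two false-discovery-rate papers appear in the reference list only. Alpha .05 appears only as an input to Power Analyses, without sidedness.

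Two passages anticipate a single directional conclusion: "evidence that parent individualized intervention beginning by 12 months of age leads to better outcomes than group education and support" (Objectives) and "substantiate that individualized intervention beginning by 12 months of age leads to better outcomes" (Expected Impact).

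The assessment ages differ by section:
- Objectives: all four domains every 6 months from 12 to 36 months, which is five ages.
- Dependent Variables: 12, 24 and 36 months, with 15 and 21 months added for social communication only.
- RQ2b: social communication and autism symptoms at 18, 24 and 36 months.

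Power Analyses gives .90 with 92 children and .86 with 80 for linear change at five time points, and calls .86 the minimum with 80.

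**The concern.** The plan looks toward one conclusion but does not say which result, or how many, would support it. With several domains, several scores in each, contrasts at unnamed ages and a second full analysis, a reader of the report cannot tell a planned test from a selected one. If one favourable score were treated as enough, the error rate of the overall conclusion would exceed that of any single test.

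The second issue is narrower. The minimum power is stated for five assessments. If the Dependent Variables schedule is the operative one, autism symptoms, developmental level and adaptive behavior have three, so the stated minimum does not cover them.

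**Working it through.** **Plan's own figures.** A single two-arm comparison at d = .50 with 46 per arm (1:1 assumed) has noncentrality .50 × √(92/4) = 2.398 and two-sided power of about .67. Averaging five measures with ICC .10 gives about .995. The stated .90 lies between these. It cannot be reproduced, because the slope variance, time scale and standardization of d are not given. It does agree with the second figure: .90 implies noncentrality 1.960 + 1.282 = 3.242; 3.242 × √(80/92) = 3.023; Φ(3.023 − 1.960) = .856, against the stated .86. Below, .90 and .86 are taken as given.

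**Error rate (illustration).** Inputs from the documents: alpha .05 and four domains. Assumptions that are not in the documents: two-sided tests, no true effect, one score per domain tested once, any one favourable result counting as support, and a common correlation r between test statistics.

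- Independent scores: 1 − .975⁴ = .096.
- Correlated scores: 1 − ∫ φ(u) · Φ[(1.96 − √r·u)/√(1 − r)]⁴ du.

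| r | 0 | .3 | .5 | .7 | .8 | .9 |
|---|---|---|---|---|---|---|
| chance of at least one false favourable result | 9.6% | 8.7% | 7.8% | 6.5% | 5.7% | 4.7% |

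A single test gives 2.5%. If all four domains had to succeed, the rate could not exceed 2.5%. If each domain is reported as its own claim, each claim keeps 2.5%.

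**Schedule and power.** When children's true slopes do not vary, the precision of a slope depends on the sum of squared age deviations:

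- 12/18/24/30/36 (mean 24): 144 + 36 + 0 + 36 + 144 = 360.
- 12/24/36 (mean 24): 144 + 0 + 144 = 288.
- 12/15/21/24/36 (mean 21.6): 92.16 + 43.56 + .36 + 5.76 + 207.36 = 349.2.

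The stated powers imply noncentralities of 3.242 (92 children) and 3.040 (80) at 360. Power is Φ(noncentrality × factor − 1.960).

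| Ages and slope variance | Factor | 92 children | 80 children |
|---|---|---|---|
| Three ages, no true slope variance | √(288/360) = .894 | .826 | .776 |
| Three ages, slope reliability .5 at five ages | √(2/2.25) = .943 | .863 | .818 |
| Three ages, slope variance dominant | 1 | .90 | .86 |
| Social communication ages, no true slope variance | √(349.2/360) = .985 | .891 | .850 |

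In the second row, the variance is 1 + 1 at five ages and 1 + 360/288 = 2.25 at three.

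**The case against.** The strongest reply is that the error-rate figure belongs to an assumed decision rule. The statements in Objectives and Expected Impact are expectations, not criteria, and nowhere is one favourable score said to be enough. This stands: the 5 to 10% is an illustration. What remains is that the rule is missing.

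Four stronger readings are tempting and are not supported:

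- *The plan has a familywise error of 10% or more.* The documents fix neither the rule, nor the sidedness, nor the correlations. Counting every instrument score as a test would give larger figures, but the Dependent Variables section describes what the instruments yield, not what will be tested.
- *Allowing residualized change or outcome only contradicts RQ1a and RQ1b.* That sentence covers all the aims and varies with the dependent variable. RQ2b concerns change, and expressive language phase is categorical. The wording is loose, not contradictory.
- *Social visual engagement cannot be both an outcome and a mediator.* A mediator has to respond to treatment, so comparing it by arm and testing it as a mediator are compatible.
- *The stated .90 is wrong.* It cannot be checked from what is given, which is a different matter.

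On the schedule, it may be said that the timeline sits in Appendix 1, which is not in the text available. That appendix could show which ages are intended, but the body text would still need correcting. It is also fair that power does not fall at all if true slopes vary greatly between children.

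**Conclusion.** The concern holds in a limited form. No Aim 1 outcome is primary, no multiplicity rule is written, and nothing says which result would support the expected conclusion. If any one of four scores sufficed at two-sided .05, the chance of a false favourable result would be about 5 to 10% instead of 2.5%. A reader might infer that this inflation is built into the plan. It is not, because other rules equally compatible with the text produce none.

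The schedule conflict does not depend on those assumptions. Objectives, RQ2b and Dependent Variables cannot all be right about the ages. Under Dependent Variables, the .90 and .86 figures, and the description of .86 as a minimum, do not apply to three of the four domains. Three ages would give about .83 to .90 with 92 children and .78 to .86 with 80, if the stated figures are correct for five equally spaced ages. The loss is modest and may be nil. Both matters should be corrected, and neither undermines the design.

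**What to change.** Before any unblinded analysis:

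1. Name one existing score and one single-parameter comparison of the arms as primary, at two-sided .05, with the model form fixed in advance. The choice is the sponsor's. It could be a mixed-model slope difference or a model-based difference at one named age.
2. List the remaining Aim 1 scores, including expressive language phase, as one secondary family under Benjamini-Hochberg at .05. State that this family does not by itself carry the primary claim; otherwise the primary test and the family together would again exceed 2.5%. Label the contrasts and Functional Data Analysis as supportive.
3. Reconcile the assessment ages in Objectives, RQ2b and Dependent Variables. Restate power, including the minimum, for any outcome with three assessments.

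The cost is a paragraph and a list of scores, with no new data. The downside is that one score carries the formal claim and the others face stricter thresholds. Depending on how subscales are counted, the listed scores number 11 (1 + 2 + 3 + 5), 13 (3 + 2 + 3 + 5) or 17 (3 + 2 + 7 + 5) for CSBS, ADOS, Mullen and Vineland. Adding expressive language phase and removing the primary leaves 11, 13 or 17. The first step is then .05/11 = .0045, .05/13 = .0038 or .05/17 = .0029. A score with the plan's .90 power at .05 would have Φ(3.242 − 2.838) = .66, Φ(3.242 − 2.890) = .64 or Φ(3.242 − 2.974) = .61 if it were the only one to succeed. The restated power may also look slightly less favourable.
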